13. PHARMACOGENETIC DATA ANALYSES

Any pharmacogenetic analyses will be described in a separate pharmacogenetic analysis plan and will be reported separately from the main clinical study report.

15. APPENDICES

15.1. Appendix 1: Countries by Region

Country	Region for Randomization Stratification
Canada USA	US/Canada
Argentina Brazil Chile Colombia Mexico Peru Puerto Rico	Central America/South America/Mexico
Australia Bulgaria Croatia Czech Republic Estonia Hungary Israel Italy Lithuania New Zealand Norway Poland Portugal Romania Russia Serbia Slovakia Spain Switzerland Turkey Ukraine	Europe/Australia/Israel
China Hong Kong India Indonesia Korea Malaysia Philippines Taiwan Thailand	Asia

15.2. Appendix 2: SELENA SLEDAI Organ System Domains

SELENA SLEDAI Organ System Domains		

SELENA SLEDAI assessments consist of 24 individual weighted items in which signs and symptoms, laboratory tests, and physician’s assessment for each of 8 organ systems are given a weighted score and summed if present (marked ‘Yes’) at the time of the visit or in the preceding 10 days. The maximum theoretical score is 105 (all 24 descriptors present simultaneously) with 0 indicating inactive disease (marked ‘No’), but in practice few subjects have scores >45 [Buyon, 2005; Petri, 2005].
 
Organ system domain scores are the sum of the weights of items within the organ domain as defined in the table below.
 
In the eCRF, laboratory items on the SLEDAI may also be ticked ‘unknown’ to indicate the lab test was not available. The laboratory items are: urinary casts, hematuria, proteinuria, pyuria, low complement, increased DNA binding, thrombocytopenia, and leukopenia.
 
List of organ systems, items, and weights for the assessments are provided.
		
Organ System	Descriptor	Weight
[1] CNS	Seizure	8
	Psychosis	8
	Organic Brain Syndrome	8
	Visual Disturbance	8
	Cranial Nerve Disorder	8
	Lupus Headache	8
	CVA	8
[2] Vascular	Vasculitis	8
[3] Musculoskeletal	Arthritis	4
	Myositis	4
[4] Renal	Urinary Casts	4
	Hematuria	4
	Proteinuria	4
	Pyuria	4
[5] Mucocutaneous	Rash	2
	Alopecia	2
	Mucosal Ulcers	2
[6] Cardiovascular & Respiratory	Pleurisy	2
	Pericarditis	2
[7] Immunologic	Low Complement	2
	Increased DNA Binding	2
[8] Hematologic	Thrombocytopenia	1
	Leukopenia	1
[9] Constitutional	Fever	1

15.3. Appendix 3: SLE Allowable Medication Categories

Medication Category	Rule
Anti-malarials	Set to "ANTIMALARIALS" if the preferred term begins with "QUINACRINE", "QUININE", "HYDROXYCHLOROQUINE", "MEPACRINE", or "CHLOROQUINE" AND the route of administration is not 'TOPICAL', 'VAGINAL', 'CONJUNCTIVAL', 'INTRANASAL', 'INHALATION', 'INTRA-OCULAR', 'INTRATRACHEAL', 'EPIDURAL', 'INTRA-ARTICULAR', or 'OTHER'.
Steroids	Set to 'STEROIDS' if at least one associated ATC code (ATCCD1 – ATCCD6) begins with 'H02' AND Route of administration is "INTRADERMAL", "INTRAMUSCULAR", "INTRAVENOUS", "ORAL", "SUBCUTANEOUS", or "INTRA-ARTICULAR".
Immunosuppressants	Set to 'IMMUNOSUPPRESSANTS' if at least one associated ATC code (ATCCD1 – ATCCD6) begins with 'L04A' or the preferred term begins with "CYCLOPHOSPHAMIDE" (oral and parenteral routes) or "MERCAPTOPYRINE" (oral route).
NSAIDs	Set to NSAIDs if at least one associated ATC code (ATCCD1 – ATCCD6) begins with 'M01A'.
Aspirin	Set to "ASPIRIN" if CMDECOD contains "ACETYLSALICYLIC ACID" or "ACETYLSALICYLATE LYSINE".
Prohibited	Set to "PROHIBITED" if any of the following conditions are met, if CMDECOD equals "INVESTIGATIONAL DRUG", "IMMUNOGLOBULIN", "ADALIMUMAB", "ETANERCEPT", "INFLIXIMAB", "RITUXIMAB", "ABATACEPT", "ANAKINRA", "GOLIMUMAB", "CERTOLIZUMAB" or "BELIMUMAB".

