9.5.17. Immunomodulatory Medications

Immunomodulatory medications are identified as all immunosuppressants with ATC code beginning “L04A” plus cyclophosphamide and mercaptopurine. For further detail see [Appendix 3](#): SLE Allowable Medication Categories.

Only immunomodulatory medication used to treat SLE will be included in summary tables of immunomodulatory medication usage (with the exception of the concomitant medication summaries which will include all medications). These are identified as those with a medication type of treatment for SLE (SDTM.CM.CMCAT = ‘SYSTEMIC LUPUS ERYTHEMATOSUS’).

It will be determined whether immunomodulatory agents are being received at any given reference date by using medication start and stop dates as follows:

- Start date and stop date are prior to reference date → subject is not on immunomodulatory agents
- Start date on or before date and stop date on or after reference date → subject is on immunomodulatory agents
- Start date on or before reference date, stop date is missing and medication is ongoing → subject is on immunomodulatory agents

Status of immunomodulatory medication is assessed at the following dates (i.e. these are the reference dates for the above derivation):

- Baseline
- Treatment completion date in treatment completers (Section [9.5.7](#))

It is also assessed for shift tables from baseline to:

- Treatment completion date (treatment completers)
- Study agent discontinuation date (subjects who prematurely discontinued study agent)

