12.1. Major Efficacy Analyses

12.1.1. Percent of Subjects with Prednisone Reduction by $\geq 25\%$ from baseline to ≤ 7.5 mg/day during Week 40 through Week 52

Primary Analysis

For this analysis, only steroids used to treat SLE will be included and only subjects with a baseline average daily prednisone dose >7.5 mg/day will be included. See Section 9.5.16.1 for derivation of baseline prednisone dose and Section 9.5.16.2 for derivation of average prednisone use between Week 40 to Week 52.

The percent of subjects whose average prednisone dose has been reduced by $\geq 25\%$ from baseline to ≤ 7.5 mg/day during Weeks 40 through 52 will be compared between belimumab and placebo using a logistic regression model. Independent variables in the model will include treatment group, baseline prednisone dose, and the following

randomization stratification factors per the eCRF: screening SELENA SLEDAI score (≤ 9 vs. ≥ 10), and region. A responder is defined as having a prednisone reduction by $\geq 25\%$ from baseline to ≤ 7.5 mg/day during Weeks 40 through 52.

Any subject who withdraws from the study or adds new immunomodulatory agents used to treat SLE (note that this will include switches) prior to the Week 52 visit will be considered having no steroid reduction.

A summary of the number and percentage of subjects who are responders by treatment group, the treatment difference versus placebo, the odds ratio and 95% CI versus placebo, and a p-value for the odds ratio will also be provided.

Sensitivity Analysis

- To examine the robustness of the results, a sensitivity analysis of the SLE-related steroid reduction will be performed without considering any information related to the use of new immunomodulatory agents (note that this will include switches).

Additional Summaries of Prednisone

- A summary of the number and percentage of subjects with average SLE-related daily prednisone dose ≤ 7.5 mg/day and > 7.5 mg/day at baseline (Day 1) and treatment completion date will be presented for treatment completers.
- The cumulative SLE-related prednisone dose will be derived as described in Section 9.5.16.3. A table of descriptive statistics will be presented including the mean, standard deviation, median, 25th and 75th percentiles, minimum and maximum.
- A listing of cumulative SLE-related prednisone dose will be displayed by treatment and subject.

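### In Appendix 3 of the Week 52 SAP the L04A branch of the immunosuppressant rule has no route condition and the mercaptopurine search term is misprinted, so the non-response flag in the major efficacy endpoint can misclassify subjects

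*SAP*

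**What the plan says.** The SAP file holds two plans; this point concerns the Week 52 plan.

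- **The consequence.** Under Section 12.1.1, a subject who withdraws or "adds new immunomodulatory agents used to treat SLE (note that this will include switches") before the Week 52 visit is treated as having no steroid reduction. Section 2.2.3 adds that the reason for a switch makes no difference, because the eCRF does not collect it.
- **The definition.** Section 9.5.17 says: "Immunomodulatory medications are identified as all immunosuppressants with ATC code beginning" L04A, with cyclophosphamide and mercaptopurine added by name. It then refers to Appendix 3 for detail. Use for SLE is identified by the recorded medication type.
- **The operative rule.** The immunosuppressant row of Appendix 3 takes a drug when at least one of up to six associated ATC codes "begins with 'L04A' or the preferred term begins with" one of two names: cyclophosphamide, limited to oral and parenteral use, or the mercaptopurine term, printed "MERCAPTOPYRINE" and limited to oral use.
- **Neighbouring rows.** The anti-malarial row adds "AND the route of administration is not 'TOPICAL', 'VAGINAL', 'CONJUNCTIVAL" and further local routes. The steroid row adds "AND Route of administration is 'INTRADERMAL', 'INTRAMUSCULAR', 'INTRAVENOUS', 'ORAL', 'SUBCUTANEOUS', or 'INTRA-ARTICULAR".
- **Sensitivity analysis.** Section 12.1.1 also plans an analysis that ignores all information on new immunomodulators.

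**The concern.** The Appendix 3 flag decides outcomes. A new SLE immunomodulator turns a steroid responder into a non-responder, with no exception by reason. A rule with that effect should pick out the drugs it is meant to pick out and no others.

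The printed rule can fail in two directions. It can count a locally applied product as escalation of systemic treatment, which lowers the responder rate. It can also miss a systemic drug that the plan names as a trigger, which raises the rate. Mercaptopurine is an expected drug in this trial: inclusion criterion 4 (Protocol Section 4.1) lists 6-mercaptopurine among the permitted background agents. The same classification feeds the separate endpoint of immunomodulator use (Section 12.2.1).

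**Working it through.** The plan states no figure here that could be reproduced. The check is a reading of the rule, its application to example records, and a note on size.

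**Step 1. Route conditions in Appendix 3, side by side**

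| Rule | Route condition |
|---|---|
| Anti-malarials | Excludes ten routes, including topical, conjunctival, intranasal, inhalation and intra-ocular |
| Steroids | Only six listed routes qualify; topical is not one |
| Immunosuppressants: L04A code | None |
| Immunosuppressants: cyclophosphamide | Oral and parenteral |
| Immunosuppressants: mercaptopurine | Oral |
| NSAIDs, aspirin | None |

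Within the immunosuppressant row, one branch of three is open. The NSAID and aspirin rows are open too, but they do not trigger non-response.

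**Step 2. Could an L04A code sit on a locally applied product?** The documents do not show such a record. They do show that the plan does not rely on an ATC code to settle route: the steroid row puts a route list on top of the H02 code, and Appendix 4 repeats the H02 code and again excludes topical routes. That would be needless if a code already fixed the route. Because any one of up to six codes is enough, a local product with an L04A code is possible. The SLE filter in Section 9.5.17 screens medication type, not route, so it does not remove such a product when it is recorded as lupus treatment.

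**Step 3. The search term.** MERCAPTOPURINE and MERCAPTOPYRINE agree on the first nine letters and differ at the tenth (U against Y). A begins-with match on the printed term therefore finds no correctly spelt record. Sections 2.2.3 and 9.5.17 name mercaptopurine as an addition to L04A, so the plan does not count on the L04A branch to capture it.

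**Step 4. The printed rule applied to example records.** The amended rule corrects the spelling and restricts the L04A branch to systemic routes.

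| Example record | Printed rule | Amended rule |
|---|---|---|
| Oral mercaptopurine, no L04A code | Not flagged | Flagged |
| Topical agent with an L04A code | Flagged | Not flagged |
| Oral agent with an L04A code | Flagged | Flagged |
| Intravenous cyclophosphamide | Flagged | Flagged |
| Topical cyclophosphamide, no L04A code | Not flagged | Not flagged |
| Topical agent, no L04A code | Not flagged | Not flagged |

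Only the first two records change.

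**Step 5. Size.** For the route gap, the fall in an arm's responder rate is

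(share of the arm that newly starts a flagged local product) × (share of those subjects who would otherwise have responded).

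The documents give neither input. To show scale only, assume 1% to 3% for the first and 15% to 20% for the second:

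- low: 1% × 15% = 0.15 percentage points;
- high: 3% × 20% = 0.6 percentage points.

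On these assumptions, the largest distortion of the difference between arms is 0.6 points, reached if all such use falls in one arm. With equal use and equal response the distortion cancels. Missed mercaptopurine works in the opposite direction and cannot be sized.

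**The case against.** The case for leaving this alone is substantial.

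- **The printed term may be harmless.** It could be a typing slip or an artefact of reading the PDF. Two body sections spell the drug correctly, Appendix 3 is a specification and not the program, and a programmer would probably have noticed. This stands as a reason to expect little effect. It does not make the printed term right.
- **The route gap needs a chain of conditions.** The product must carry an L04A code, be recorded as SLE treatment and be new, and the subject must otherwise be a responder. Coding follows the sponsor's drug dictionary (Section 10.4), which is not supplied. This also stands: the consequence is possible, not shown.
- **The sensitivity analysis drops the flag.** True, but it discards genuine escalation together with any misclassification, so it cannot isolate the error. Appendix 4 promises a review of steroid terms and routes at database release; no matching review is stated for immunosuppressants.

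A reader might also be tempted to infer more than the text supports:

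- *That the rule has no route limit at all.* Two of its three branches have one.
- *That the misclassification follows treatment and so biases the comparison.* Nothing in the documents shows that local products are started more often in one arm.
- *That every subject adding mercaptopurine escapes.* That requires the printed term to have been programmed as it stands and the record to carry no L04A code. Neither is shown.
- *That moving from a topical to an oral form of the same drug would not count as new.* The plan does not define new by drug or by route, so this cannot be read from it.

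**Conclusion.** The point holds as a minor specification defect with two parts: an L04A branch without a route condition, next to branches and rows that have one, and a misprinted mercaptopurine term. Followed literally, the first can create false non-responders and the second can leave false responders in the major efficacy endpoint and distort the summaries of immunomodulator use.

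The size is unknown because the documents give no count of such records. It is probably small; the 0.15 to 0.6 points above rest entirely on assumed inputs. The conclusion assumes that the program follows the printed rule and that at least some records of either kind exist. Mortality, the adverse events of special interest and the other primary safety analyses do not use this flag and are unaffected.

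**What to change.** 1. For the non-responder rule in Section 12.1.1 and the immunomodulator summaries in Section 12.2.1, exclude local routes from the L04A branch. The topical, conjunctival, intranasal, inhalation and intra-ocular routes in the anti-malarial row are a ready list.
2. Keep L04A records with a missing route, so that systemic agents are not dropped. An exclusion list does this; an inclusion list would not. If a systemic list is preferred, the five-route list is in Section 9.5.16 and Appendix 4. The Appendix 3 steroid row differs because it also admits intra-articular use.
3. Correct the search term to MERCAPTOPURINE.

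Before unblinding, this would have cost one added condition and one corrected string. The follow-up plan (Section 1) gives unblinding as 2-JAN-2019 and completion of the statistical analysis as 7-FEB-2019. The remaining step is therefore to look at the program, count the records that change class in each arm, and report the responder analysis with the corrected flag beside the one already produced. If no record changes, a one-line statement closes the matter. No new data are needed.

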15.4. Appendix 4: Prednisone Equivalent Conversion

- A concomitant medication is identified as a steroid if at least one associated ATC code (ATCCD1 – ATCCD6) begins with ‘H02.’
- The following routes are considered to provide systemic exposure: oral, subcutaneous, intramuscular, intradermal, and intravenous. Topical routes of administration are excluded (e.g., topical, conjunctival, intranasal).
- At data base release, all preferred terms identified with an ATC code beginning with ‘H02’ will be reviewed to ensure a conversion factor exists for all terms with a systemic route of administration.
- Similarly, all routes of administration for preferred terms with an ATC code beginning with ‘H02’ will be reviewed to ensure all systemic routes have been identified in the list above.
- In order to be converted the frequency and dose of the steroid must be present with the unit dose in milligrams (mg).
- Reported dose for systemic steroid is converted to prednisone equivalent dose using conversion factor for each particular medication (refer to online calculator <http://www.globalrph.com/corticocalc.htm>).

A two-step process will be used to calculate the prednisone equivalent daily dose:

1. $DOSE2$ (prednisone equivalent dose in mg) = $DOSE$ (collected dose in mg) x Conversion Factor
2. DD (daily dose in mg/day) = $DOSE2$ (prednisone equivalent dose in mg) x Frequency Factor

Where multiple steroids are taken on one day, the sum of these will be the prednisone equivalent daily dose. An intermediate dataset will contain the total daily prednisone equivalent daily dose for each study day. This will be used to derive prednisone endpoints.

Preferred term	Conversion factor for converting to a prednisone-equivalent dose
BETAMETHASONE	8.333
BETAMETHASONE DIPROPIONATE	8.333
BETAMETHASONE SODIUM PHOSPHATE	8.333
BETAMETHASONE VAL	8.333
BETROSPAM	8.333
CELESTONA BIFAS	8.333
CORTISONE	0.2
CORTISONE ACETATE	0.2
CRONOLEVEL	8.333
DEFLAZACORT	0.8333
DEPO-MEDROL MED LIDOKAIN	1.25
DEXAMETHASONE	6.667

Preferred term	Conversion factor for converting to a prednisone-equivalent dose
DEXAMETHASONE ACETATE	6.667
DEXAMETHASONE PHOSPHATE	6.667
DEXAMETHASONE SODIUM PHOSPHATE	6.667
FLUCORTOLONE	3
HYDROCORTISONE	0.25
HYDROCORTISONE ACETATE	0.25
HYDROCORTISONE HYDROGEN SUCCINATE	0.25
HYDROCORTISONE SODIUM SUCCINATE	0.25
MEPREDNISONE	1.25
METHYLPREDNISOLONE	1.25
METHYLPREDNISOLONE ACEP	1.25
METHYLPREDNISOLONE ACETATE	1.25
METHYLPREDNISOLONE HEMISUCCINATE	1.25
METHYLPREDNISOLONE SODIUM SUCCINATE	1.25
PARAMETHASONE	2.5
PREDNISOLONE	1
PREDNISOLONE SODIUM PHOSPHATE	1
PREDNISOLONE SODIUM SUCCINATE	1
PREDNISONE	1
PREDNISONE ACETATE	1
TRIAMCINOLONE	1.25
TRIAMCINOLONE ACETATE	1.25
TRIAMCINOLONE ACETONIDE	1.25

Frequency Factors	
Frequency	Factor
BID	2
BIW	2/7
OAM	1/30
OD	1
Once	1
PRN	Null
Q2H	12
Q2W	1/14
Q3H	8
Q3D	1/3
Q3MO	1/84
Q3W	1/21
Q4H	6
Q4D	1/4
Q4W	1/28
Q6H	4
Q8H	3

[figure not shown]
Frequency Factors	
Frequency	Factor
Q12H	2
QAM	1
QD	1
QH	24
QHS	1
QID	4
QOD	½
QPM	1
QW	1/7
QWK	1/7
QM	1/30
TID	3
TIW	3/7
UNK	Null
2 TIMES PER WEEK	2/7
3 TIMES PER WEEK	3/7
4 TIMES PER WEEK	4/7
EVERY 2 WEEKS	1/14
EVERY 3 WEEKS	1/21
EVERY 4 WEEKS	1/28
EVERY WEEK	1/7

Unit Conversion Factors	
Unit	Factor
MCG	0.001
G	1000
MG/DAY	1
OZ	28349.5
UG	0.001
MG	1

Any additions to the conversion factors or frequency factors noted above, that are identified during final data reconciliation but after RAP approval, will be documented prior to unblinding the study.

15.5. Appendix 5: SLICC/ACR Damage Index

CCI - This section contained Clinical Outcome Assessment data collection questionnaires or indices, which are protected by third party copyright laws and therefore have been excluded.

Item	Score
Musculoskeletal	
Muscle atrophy or weakness	1
Deforming or erosive arthritis (including reducible deformities, excluding avascular necrosis)	1
Osteoporosis with fracture or vertebral collapse (excluding avascular necrosis)	1
Avascular necrosis (score 2 if > 1)	1(2)
Osteomyelitis	1
Skin	
Scarring chronic alopecia	1
Extensive scarring or panniculum other than scalp and pulp space	1
Skin ulceration (excluding thrombosis) for > 6 months	1
Premature gonadal failure	
	1
Diabetes (regardless of treatment)	
	1
Malignancy (exclude dysplasia) (score 2 if > 1 site)	
	1(2)

(From the Systemic Lupus International Collaborating Clinics (SLICC) and the American College of Rheumatology Diagnostic and Therapeutic Criteria Committee, 1996)

15.6. Appendix 6: PSAP Sections for AESI Reporting

Section 15: Adverse Events of Special Interest

AESI are defined using preferred terms from the current version of MedDRA. The intent is to update these definitions semi-annually using the newest MedDRA version. Preferred terms used in the current and prior versions of MedDRA can be found in [Section 17](#).

Section 15.1: Malignant neoplasms

Malignant neoplasms are identified using the sub-SMQs of Malignant or unspecified tumours (20000091), malignancy related conditions (20000092), haematological malignant tumours (20000227), non-haematological malignant tumours (20000228), haematological tumours of unspecified malignancy (20000229) and non-haematological tumours of unspecified malignancy (20000230) under the current version of MedDRA. The sub-SMQ of Malignant or unspecified tumours contains two further subcategories: “Malignant Tumours” and “Tumours of unspecified malignancy.” Tumours of unspecified malignancy will be reviewed by GSK and identified as malignant or non-malignant for reporting.

Malignancies other than those in the “Tumours of unspecified malignancy” category will be categorized as hematologic, skin, or solid, based on a CMQ developed by the MAH ([Section 17.1](#)). In addition, the following customizations have been made (generally since MedDRA v19.1).

The following terms have been added as hematological tumour types:

- Marginal zone lymphoma recurrent
- Epstein Barr virus positive mucocutaneous ulcer
- Primary gastrointestinal follicular lymphoma
- Transformation to acute myeloid leukaemia
- FIP1L1/PDGFR alpha fusion kinase positive
- Acute bilineal leukaemia
- Primary breast lymphoma

The following terms have been added as a solid tumour type:

- Malignant meningioma metastatic
- Astroblastoma
- Langerhans cell sarcoma
- Nasopharyngeal cancer metastatic
- Phosphaturic mesenchymal tumour
- Squamous cell breast carcinoma

Gleason grading score
Oncotype test
Malignant urinary tract obstruction
Sarcomatoid carcinoma
Cystadenocarcinoma pancreas
Paracancerous pneumonia
Chromophobe renal cell carcinoma
Gastrointestinal adenocarcinoma
Pleuropulmonary blastoma
Primary pulmonary melanoma
Dysplastic naevus
ALK gene rearrangement positive
Breast tumour excision
NMP22 test abnormal

The following terms have been added as a skin tumour type:

Naevoid melanoma
Trichoblastic carcinoma

The following terms have been added as a tumour of unspecified malignancy:

Mismatch repair cancer syndrome
Skin neoplasm bleeding
Intestinal metastasis
Maternal cancer in pregnancy
Microsatellite instability cancer
Pulmonary tumour thrombotic microangiopathy
Tumour cavitation
Tumour hyperprogression
Paraneoplastic myelopathy
Carcinogenicity
BRAF V600E mutation positive
Paraneoplastic thrombosis

In addition, the preferred term “Malignant neoplasm progression” was moved from “Non-haematological Malignant Tumour” SMQ in MedDRA Version 20.1 to “Malignancy Related Conditions” SMQ in MedDRA Version 21.0, and was further customized to be a tumour of unspecified malignancy.

The following terms have been removed from the SMQ:

Paraneoplastic glomerulonephritis (as it is a complication of malignancy)

Lymphoma cutis

Mucinous cystadenocarcinoma of pancreas

Serous cystadenocarcinoma of pancreas

Secondary cerebellar degeneration

Bone marrow infiltration

Pseudoachalasia

Malignant exophthalmos

Tumour obstruction

Tumour psuedoprogession

Paraneoplastic arthritis

Tumour pruritus

Oncogenic osteomalacia

Neurogenic tumour

Non-melanoma skin cancer (NMSC) will be categorized using a CMQ developed by the Marketing Authorization Holder (MAH) ([Section 17.1](#)).

Note beginning with MedDRA v20.0 in 2017, there will be two new sub-SMQs of Hematological Malignancies. These do not result in any changes to how malignant neoplasms are identified.

Post-study malignancies that are captured in ARGUS prior to CSR approval, but are not captured in the clinical database, will be described within the CSR text but cannot be included in statistical post-text displays. Post-study malignancies are not adjudicated by the SRT.

Additionally, for the BEL115467 “BASE” study, any malignancies that are reported annually (in the Year 2-5 post-treatment follow-up) via malignancy status updates in the CRF and not captured in ARGUS, will not be adjudicated by the SRT.

Section 15.2: Post-infusion/injection systemic reactions

Post-infusion/injection systemic reactions will be identified using a customization of the Anaphylactic Reaction SMQ (20000021). This SMQ includes a broad list of preferred terms including symptoms of systemic injection/infusion reactions and hypersensitivity reactions and anaphylaxis. For the Anaphylactic Reaction query, 4 categories of preferred terms are considered, including a set of core anaphylactic terms (Category A), upper airway/respiratory terms (Category B), angioedema/urticaria/pruritus/flush terms (Category C), and cardiovascular/hypotension terms (Category D).

The customizations of the SMQ involve terms in Categories A, B and C:

- Category A has been modified to include the following additional terms: “Infusion-related reaction”, “Drug hypersensitivity”, “Hypersensitivity”, and “Urticarial vasculitis”.
- Category B has been modified to include the following additional terms: “Oropharyngeal oedema” and “Pharyngeal oedema”.
- Category C has been modified to include the following additional terms: “Fixed eruption”, “Drug eruption” and “Lipoedema”.

GSK has also removed eight terms that are not relevant for an analysis of hypersensitivity reactions to belimumab (“Anaphylactic transfusion reaction”, “Dialysis membrane reaction”, “Cyanosis”, “Nasal obstruction”, “Ocular hyperaemia”, “Tachypnoea”, “Hereditary angioderma with C1 est” and “Acquired C1 inhibitor deficiency”).

- Anaphylactic transfusion reaction is an adverse event associated with a blood transfusion, not related to study medication.
- Dialysis membrane reaction is associated with adverse events related to kidney transplants and dialysis, not related to study medication.
- Cyanosis, nasal obstruction, ocular hyperaemia, tachypnoea, hereditary angioderma with C1 est, acquired C1 inhibitor deficiency are adverse events generally not associated with post-infusion/injection systemic reactions.

The terms “Injection site urticaria”, “Eye pruritis”, and “Procedural shock” are part of the Anaphylactic Reaction SMQ but were inadvertently excluded (identified during PSAP Version 6 update). These terms will be included when the next MedDRA version i.e. MedDRA Version 21.1. is released.

Algorithmic Search Criteria

The post-infusion/injection systemic reactions per Anaphylactic Reaction SMQ algorithmic search are defined as follows:

Subjects must have the following associated with the same infusion/injection:

- a. at least 1 AE coding to a Category A preferred term *or*

- b. 2 AEs, 1 coding to a Category B preferred term and the other coding to a Category C preferred term *or*
- c. 2 AEs, 1 coding to a Category D preferred term and the other coding to either a Category B preferred term or to a Category C preferred term.

For the algorithmic search, if any event at a given infusion/injection meets the definition under criteria a, b or c, then all events in Categories A, B, C and D associated with that injection/infusion will be considered AESI.

GSK SRT will review all serious events identified via the broad search using a 21-day window from the start of an infusion/injection (see PSAP Section 8.3.2 for the definition of the assessment windows), and adjudicate these events as post-infusion/injection systemic reactions or hypersensitivity reactions per the criteria in [Section 16.2](#). Therefore, the window for the narrow, broad and algorithmic searches of AE and SAE data from the clinical database for SRT reporting (PSAP Section 13.3) is 21 days to correspond to the window for adjudication. Adverse events with partial or missing start dates will be included unless there is evidence through comparison of partial dates to suggest otherwise.

Note, for CSR reporting, narrow, broad, and algorithmic searches of AE and SAE data will be run using a 3-day window from the start of an infusion/injection.

Sampson Criteria

Sampson et al define anaphylaxis as a severe, potentially fatal, systemic allergic reaction that occurs suddenly after contact with an allergy-causing substance. In addition, one of the following 3 criteria must be met: (1) acute onset of illness with involvement of skin or mucosal tissue, accompanied with either respiratory compromise, reduced blood pressure, or hypotension-related symptoms of end-organ dysfunction (2) reduced blood pressure associated with a known allergen or (3) two or more of the following that occur rapidly after exposure to an allergen: a) involvement of skin-mucosal tissue b) respiratory compromise c) reduced blood pressure d) persistent GI symptoms.

With the exception of GI symptoms, all symptoms required to assess anaphylaxis per Sampson criteria would be identified by Broad Anaphylaxis SMQ or the Anaphylactic Reaction SMQ algorithmic. Therefore, any events falling under the below criteria will be adjudicated by SRT prior to database release to determine if serious anaphylaxis per Sampson criteria is met.

Possible cases of serious anaphylaxis per Sampson criteria will be identified as follows:

- a. Any Infusion/Injection-related Reaction per Anaphylactic Reaction SMQ broad search SAE which occurs during the first 24 hours after the start of an infusion/injection.
- b. Any AE or SAE in the “Gastrointestinal disorders” SOC that coincides with the event that meets the criterion in a) above.

- c. Any anaphylaxis and hypersensitivity reactions per Anaphylactic Reaction SMQ algorithmic search SAE which occurs during the first 24 hours after the start of an infusion/injection.

Section 15.3: Infections

The infections of special interest are described below.

Section 15.3.1: Opportunistic Infections

Opportunistic infections will be identified using a broad CMQ developed by the MAH (Section 17.1). Any events falling under these preferred terms will be adjudicated by GSK to determine if criteria are met for an opportunistic infection, per the criteria in Section 16.3.

Section 15.3.2: Mycobacterium Tuberculosis

Tuberculosis events will be identified using a CMQ developed by the MAH (Section 17.1). Any events falling under these preferred terms will be adjudicated by GSK to determine if criteria are met for an opportunistic infection (Section 16.3).

Section 15.3.3: Herpes Zoster

Herpes Zoster events will be identified using a CMQ developed by the MAH (Section 17.1). Additional manual adjudication by GSK will identify events that are recurrent or disseminated (Section 16.3).

Section 15.3.4: Pneumonia

Pneumonia events will be identified using a CMQ developed by the MAH (Section 17.1). Pneumonia events will not be reported separately, but are being flagged in the event further evaluation is necessary.

Section 15.3.5: Sepsis

Sepsis events will be identified using a CMQ developed by the MAH (Section 17.1).

Section 15.4: Depression/suicide/self-injury

Section 15.4.1: Depression (excluding suicide and self-injury)

Depression events will be identified using a CMQ including the preferred terms from the depression (excluding suicide and self injury) SMQ (20000167) plus additional terms added by the MAH (Section 17.1).

Section 15.4.2: Suicide and Self-Injury

Suicide and self-injury events will be identified using the SMQ (20000037) plus additional terms added by the MAH (Section 17.1).

Section 15.5: Fatalities

All fatalities that are reported while a subject is eligible for SAE reporting will be identified in the clinical database and subsequently adjudicated by the GSK SRT into a general category of death ([Section 16.5](#)).

Post-study fatalities that are captured in ARGUS prior to CSR approval, but are not captured in the clinical database, will be described within the CSR text but cannot be included in statistical post-text displays. Post-study fatalities are not adjudicated by the SRT.

Additionally, for the BEL115467 “BASE” study, any fatalities that are reported annually (in the Year 2-5 post-treatment follow-up) via survival status updates in the CRF and not captured in ARGUS, will not be adjudicated by the SRT.

Section 16: GSK SRT Adjudication of Adverse Events of Special Interest

Adverse events of special interest (AESI) are identified per the preferred terms ([Section 17.1](#)) and other criteria described in [Section 15](#). The following AESI are adjudicated in-stream at the subject level by GSK during regular SRT meetings or during quarterly adjudication, and then prior to database release for CSR reporting purposes, per the criteria described below.

In-stream review/adjudication of AESI is conducted as follows:

- Review/Adjudication of AESI in ARGUS

Safety Evaluation and Risk Management (SERM) lists all events in ARGUS each month for SRT to review. AESIs are adjudicated at SRT meetings and entered onto Excel spreadsheets maintained by SERM. These spreadsheets are cumulative and contain events for all belimumab studies (clinical trials, post-marketing studies and spontaneous reports). SERM refer to these as “Cumulative AESI spreadsheets”. SERM use these spreadsheets to tabulate the numerators used for PBRER/DSUR rates (see PSAP Section 7.6). The numerators are typically updated shortly after the Data Lock Point, and updated numerators are then used for PBRER/DSUR updates. The numerators are tracked in spreadsheets referred to as “AESI numerator spreadsheets”.

- Review/Adjudication of AESI in the Clinical Database

The SRT central programming team sends spreadsheets of AESIs based upon the CRF (Clinical Database) to SERM for periodic in-stream review. These spreadsheets contain AEs and SAEs and are study specific. SERM enter adjudication based on the SRT adjudication (“Cumulative AESI spreadsheets”) and checks for missing serious AESIs between ARGUS and the Clinical Database. SERM send the clinical data derived spreadsheets to the study specific Medical Monitor, who adjudicates the non-serious events. Once updated, the spreadsheets are returned to the SRT central

programming team and are used to create the SRT output for the next periodic in-stream review.

In addition, as part of individual study close-out procedures, the adjudications should be finalized as follows:

- Just preceding database freeze (DBF), allowing time to send queries or update the eCRF/database as necessary prior to DBF, and are used in the CSR.
- Between DBR and Source Database Lock (as required) to provide final confirmation of adjudications and ensure there are no new AESI or relevant data changes to adjudicated events since the pre-DBR adjudication. This would be a requirement for declaring database freeze (DBF).

Note, at study close-out, the study programming team is responsible for generating spreadsheets of AESIs based upon the clinical data, in consult with the SRT central programming team, and liaising with SERM to finalise the adjudication. Refer to the SRT team site for more information: SRT/Team Documents/SRT documentation/AESI/Belimumab_ADAE_AEANAL AESI Adjudication Variables Process.doc.

Section 16.1: Malignancies

All malignancies identified via the terms in [Section 17.1](#) will be reviewed by GSK SRT. The classification of malignancies as solid tumor, hematological, and skin will be reviewed against the verbatim term to confirm an appropriate and accurate preferred term has been assigned, or to recommend follow-up with the investigator for additional specificity on the verbatim term. In addition, malignancies that are flagged more than once, e.g., based on a term for both a diagnostic procedure and a diagnosis, will be adjudicated as one event.

Tumors of unspecified malignancy, as identified per the terms in [Section 17.1](#), will be reviewed clinically by the GSK SRT for reporting. In general, non-serious events in the tumours of unspecified malignancy with insufficient information will be categorized as not malignant. Serious adverse events with insufficient information will be categorized as either not malignant or malignant based on the type of tumor and likelihood the tumor type is malignant (e.g., thyroid nodules are common in SLE patients and are generally not malignant; tumor types with higher likelihood for malignancy would be assumed to be malignant).

Section 16.2: Serious hypersensitivity and post-infusion/injection systemic reactions

GSK SRT will review all serious cases identified from the Broad Anaphylaxis SMQ as described in [Section 15](#) and [Section 17.1](#), applying clinical judgment to determine if the preferred terms are indicative of a hypersensitivity or post-infusion/injection reaction. Time to onset after an infusion/injection and details provided in the clinical narratives with respect to the nature and likely cause of the events are taken into consideration. The GSK SRT adjudicates serious hypersensitivity reactions into a category based primarily on time to onset: acute (onset < 24 hours), delayed acute (onset 2-3 days), or delayed, non-acute (onset 4-21 days). In addition to time to onset, description of associated symptoms is taken into account for this categorization. In studies where subjects are

receiving weekly injections, any delayed, non-acute reactions will typically occur in the interval 4-7 days later, but may occur up to 21 days later following a missed injection or after the last injection.

In addition, possible cases of serious anaphylaxis per Sampson criteria will be identified per the criteria in [Section 15](#). Any events falling under these criteria will be adjudicated by GSK prior to database release to determine if serious anaphylaxis per Sampson criteria is met.

Section 16.3: Potential opportunistic infections

